8.2. Maintenance and storage of the device

The devices are single use. They will be stored in the anaesthetic store rooms in the operating theatre suites at the John Radcliffe, Churchill, West Wing, Women's Centre, and Nuffield Orthopaedic theatres.

9. SAFETY REPORTING**9.1. Definitions****9.1.1 Adverse Event (AE):**

An AE or adverse event is:

Any untoward medical occurrence in a patient or other clinical investigation participant taking part in a trial of a medical device, which does not necessarily have to have a causal relationship with the device under investigation.

An AE can therefore be any unfavourable and unintended sign (including an abnormal laboratory finding), symptom or disease temporally associated with the use of the device, whether or not considered related to the device.

9.1.2: Adverse Device Effect (ADE)

All untoward and unintended responses to the medical device.

The phrase "responses to a medical device" means that a causal relationship between the device under investigation and an AE is at least a reasonable possibility, i.e., the relationship cannot be ruled out.

All cases judged by either the reporting medically qualified professional or the sponsor as having a reasonable suspected causal relationship to the device qualifies as a device effect. This also includes any event resulting from insufficiencies or inadequacies in the instruction for use or deployment of the device and includes any event that is a result of a user error.

9.1.3 Serious Adverse Event (SAE):

SAE is an adverse event that

- ♣ Led to death
- ♣ Led to fetal distress, fetal death or congenital abnormality or birth defect.
- ♣ Led to serious deterioration in the health of the subject that
 - Resulted in a life-threatening illness or injury

NOTE: The term "life-threatening" in the definition of "serious" refers to an event in which the participant was at risk of death at the time of the event; it does not refer to an event which hypothetically might have caused death if it were more severe.

 - Resulted in a permanent impairment of a body structure or a body function
 - Required in-patient hospitalisation or prolongation of existing hospitalisation
 - Resulted in medical or surgical intervention to prevent permanent impairment to a body structure or a body function
 - Other important medical events*

*Other events that may not result in death, are not life threatening, or do not require hospitalisation, may be considered a serious adverse event when, based upon appropriate medical judgement, the event may jeopardise the patient and may require medical or surgical intervention to prevent one of the outcomes listed above

To ensure no confusion or misunderstanding of the difference between the terms "serious" and "severe", which are not synonymous, the following note of clarification is provided:

The term "severe" is often used to describe the intensity (severity) of a specific event (as in mild, moderate, or severe myocardial infarction); the event itself, however, may be of relatively minor medical significance (such as severe headache). This is not the same as "serious," which is based on patient/event outcome or action criteria usually associated with events that pose a threat to a participant's life or functioning. Seriousness (not severity) serves as a guide for defining regulatory reporting obligations.

9.1.4 Serious Adverse Device Effects (SADE):

A serious adverse device effect (SADE) is any untoward medical occurrence seen in a patient that can be attributed wholly or partly to the device which resulted in any of the characteristics or led to a characteristics of a Serious adverse event.

SADE is also any event that may have led to these consequences if suitable action had not been taken or intervention had not been made or if circumstances has been less opportune. All cases judged by either the reporting medically qualified professional or the sponsor.

9.1.5 Unanticipated Adverse Device Effect (UADE):

Any serious adverse device effect on health or safety or any life-threatening problem or death caused by, or associated with a device, if that effect, problem, or death was not previously identified in nature, severity or degree of incidence in the investigational plan or application (including a supplementary plan or application), or any other unanticipated serious problem associated with a device that related to the rights, safety or welfare of the subject.

9.2. Reporting of AE

All AE's occurring during the study observed by the investigator or reported by the participant, whether or not attributed to the device under investigation will be recorded on the CRF as specified in the protocol. All ADE's will be recorded in the CRF.

The following information will be recorded: description, date of onset and end date, severity, assessment of relatedness to device, other suspect drug or device and action taken. Follow-up information should be provided as necessary.

The relationship of AEs to the device will be assessed by a medically qualified investigator or the sponsor/manufacturer and will be followed up until resolution or the event is considered stable.

All ADE that result in a participant's withdrawal from the study or are present at the end of the study, should be followed up until a satisfactory resolution occurs.

Where relevant, any pregnancy occurring during the clinical study and the outcome of the pregnancy, should be recorded and followed up for congenital abnormality or birth defect.

9.3. Reporting Procedures for All SAEs/ SADEs/ UADEs

All SAE/SADE/UADEs need to be reported to the sponsor/legal representative and manufacture and OUH R&D **within one working day** of the investigator team becoming aware of them.

Reports of related and unexpected SAEs should be submitted to ethics within 15 days of the Chief Investigator becoming aware of the event, using the SAE report form for non-CTIMPs published on the NRES website.

All reporting to ORH R&D should be by email to [contact] giving as much information about the incident as possible, and should be signed by the PI or Co-investigator. The ORH SADE reporting form should be used for ORH sponsored studies.

The ORH R&D Department will undertake an initial review of the information and ensure it is reviewed by the ORH/University of Oxford Trial Safety Group Medical Monitor. Events will be followed up until resolution, any appropriate further information will be sent by the research team in a timely manner.

Reporting to the MHRA will be done in liaison with the Chief Investigator and the Manufacturer.

The Manufacturer has a legal obligation to report all events that need to be reported to the Nominated Competent Authority immediately (without any unjustifiable delay) after a link is established between the event and the device, but no more than:

- ♣ 2 days following the awareness of the event for Serious Public Health Threat.
- ♣ 10 days following awareness of the event for Death or unanticipated serious deterioration in health.
- ♣ 30 days following the awareness of the event for all other event meeting the SAE criteria.

9.4. Annual Reports

In addition to the above reporting the Chief Investigator will submit once a year, throughout the trial, or on request a progress/safety report to the REC and R&D.

10. STATISTICS AND ANALYSIS

10.1. Description of Statistical Methods

The data in this single arm study will be described by descriptive statistics only, using binomial confidence where necessary.

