The LMA® Protector™ is CE marked, produced in a number of sizes, and has been marketed for clinical use since mid-2016, without any design changes until now, and there is as yet only limited trial data on its use beyond pilot studies (14). Given the enhanced design of the LMA® Protector™ there are clear potential advantages to its use, and trial data is required to determine its safety and efficacy. In order to fulfil the ADEPT guidance minimum standard of evidence the device must be further evaluated before it may be safely recommended for purchase by hospital trusts in the UK. We propose a national multi-centre prospective controlled clinical evaluation cohort study, as sufficient to delineate the performance of the device and determine its likely place in clinical practice in the UK (or similar) rather than presupposing we will "recommend it". The LMA® Protector™ is not used in standard care in any of the hospital trusts involved in the study.

Study outline and research questions

We will conduct a prospective multi-centre cohort study to evaluate the performance of the device. The main research questions pertain to the device performance, focusing on quality of the airway, ease of insertion, quality of ventilation, and incidence of complications.

Participants

All patients aged above 18, ASA grade 1 to 3, presenting for elective surgical procedures and requiring and suitable for a supraglottic airway device will be invited to take part in the study. Exclusion criteria are: a) patient refusal, b) below 18 years of age, c) requiring intubation, d) risk factors for aspiration, e) ASA 4 and above, f) mouth opening of less than 2.5cm and deemed to require awake intubation.

Potential risks

The potential risks and burdens are the same compared to using other airway devices during anaesthesia. We will minimise them by ensuring adequate training in the use of the device is used, by recruiting investigators who are anaesthetists with experience of using similar airway devices more than 200 times.

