5. STUDY DESIGN

This is a prospective, multi-centred cohort observational study, where all suitable participants will have the LMA Protector used. The centres involved will be: Oxford University Hospitals NHS Foundation Trust, Northampton General Hospital, Royal Berkshire Hospital, Royal United Hospital, and University Hospital of Wales. The participants will be involved in the study for maximum 48 hours starting from approach for consent on the morning of surgery, while they are in the pre-operative area, until the second interview (either in person if participant is an inpatient, or via telephone if participant had been discharged). Data will be collected while the anaesthetic is being conducted apart from the information regarding the complications of the device removal and postoperatively. The order of events will be: a) consent, b) general anaesthetic as per standard care but using LMA protector, c) brief interview by clinician following operation in hospital at first available opportunity, d) another interview 24 to 48 hours later with the same questions either in hospital or at home by telephone.

Data that will be collected will be: a) investigator name, b) number of previous insertions of the device by the investigator, c) patient age, d) patient gender, e) weight, f) height, g) ASA class, h) operation, i) anaesthetic drugs and dosages, j) anaesthetic technique, k) mode of ventilation, l) if further muscle relaxant used. Moreover, we will collect:

- 1) Airway assessment including Malampatti classification
- 2) The number of attempts at the insertion will be recorded

- 3) Volume of air in cuff to achieve intracuff pressure of 60cmH₂O
- 4) Airway leak pressure
- 5) The ease of insertion
- 6) The lowest oxygen saturation recording
- 7) The quality of ventilation
- 8) The quality of the airway during maintenance
- 9) The ease of hands free anaesthesia
- 10) The overall usefulness of the device in the patient
- 11) The overall performance of the device
- 12) The time to first square capnography trace
- 13) Positive or negative bubble test
- 14) Airway manipulations to establish airway
- 15) Complications on insertion, during use, and on removal of the device
- 16) Post-operative oropharyngeal sequelae

The data will be collected from the anaesthetic record. Data c, d, e, f will be collected from the electronic notes.

All data will be recorded in the CRF/data collection form.

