7.2. Screening and Eligibility Assessment

On the morning of surgery, the investigator will examine their operating list and decide if the operations are suitable for the LMA Protector. The investigator will be a member of the direct care team, i.e. the anaesthetist for the case.

If the patients do not meet any exclusion criteria then they will be asked whether they wanted to participate in the study, the PIL will be given to them and they will be given at least one hour to make up their mind. The investigator will then approach the patient again, answer any remaining questions and obtain informed consent.

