10.2. The Number of Participants

We will recruit 1100 - 2000 patients with an interim analysis at 1100 patients.

The sample size is based on the paper:

Pandit JJ. If it hasn't failed, does it work? On 'the worst we can expect' from observational trial results, with reference to airway management devices. *Anaesthesia*. 2012 Jun;67(6):578-83. That explains how binomial confidence intervals can be used in observational airway research of this type.

The conclusions were:

- Investigators in observational studies should state what they regard as 'success' or 'failure' of using the device in question. Where the main endpoint is a continuous variable, researchers should define a justifiable threshold so that it can also be described as a categorical (binomial) endpoint,
- For all results, the upper limit of the 95% confidence interval (CI) should be quoted,
- For airway devices such as SADs, a 95% CI upper limit failure rate $> 2.5\%$ ('the worst we can expect') in the chosen endpoint should generally lead to a conclusion that the device is poor or unsuitable for clinical use, compared with established devices,
- In planning an observational trial, the minimum sample size should be calculated to yield (99% CI) for at least one failure of the device, which generally means that sample sizes should exceed 250,
- Observational studies with < 250 patients are unlikely to provide useful evidence in favour of a device's clinical acceptability, although they may provide useful information suggestive of its lack of acceptability.

We followed all of these conclusions and our expected 1100 recruited patients are a lot more than the 250 expected to show a 2.5% failure rate with 95% CI.

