10.3. Analysis of Outcome Measures

The study will recruit up to 2000 patients, with an interim analysis at 1100 looking at the device failure rate. This is an observational study only. If we apply binomial confidence intervals according to the reference cited, and assume a 'failure rate' of clinical importance as 5%, we find an upper limit 95% CI of 6.54% with 1000 patients. For 2000 patients this upper limit is 6.05%. Thus, the gain of precision in studying up to 2000 patients may be very marginal if this is what an interim analysis at 1100 patients shows. We will however, continue the study if the 'failure rate' is >10% as then the precision in estimate benefit of studying 2000 patients is greater.

The data in this single arm study will be described by descriptive statistics only, using binomial confidence where necessary.

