13.7. Other Ethical Considerations

There are no other ethical issues involved in this study.

14. FINANCE AND INSURANCE**14.1. Funding**

The study is funded to the requested sum of £56,400, £20,000 of which would be paid immediately for consumables and the rest to be held as a contingency if needed, and there is no time limit although DAS reserves the right to withdraw the funds from January 2022. Costs of devices are covered by a grant from the Difficult Airway Society (DAS) to the University of Oxford for the sum of £15,400. The rest of the grant money is for a PhD through DAS and has no bearing with the funds available for the study. We are awaiting an invoice from DAS that soon should be raised and we will (via the university) pay this sum over to them, soon after which the devices will arrive.

Each research site will obtain the devices directly from the central store area. The orders will be placed with the company Teleflex, and on the orders will be specified which site to send the devices to. Once the order is placed the company will ship them as required.

Each researcher is a consultant with an NHS contract. This consists of Direct Care Programmed Activities (DCC) and Supporting Professional Activity (SPA). The latter is, within the contract, up to 10 hours per week, and is assigned to activities including research and quality improvement. If a consultant does not deliver on these goals or use that paid time for these activities s/he is in breach of contract. Moreover, if they seek or take additional payment for these activities then they are being paid twice for the same work which is illegal. Moreover, the use of SPA time (up to 10 hours/wk) in any given year is specified at Appraisal which is a mandatory and directional meeting to assign goals for the coming year. Therefore, this project is explicitly factored in to the fully funded development goals.

A study coordinator will be put in place covered by funding from the Difficult Airway society.

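### The planned binomial limits treat every insertion as independent. If outcomes cluster by anaesthetist the upper 95% limit can be too low, and one added operator-clustered interval would show by how much.

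*Combined protocol and SAP*

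**What the plan says.** Section 10.1 states the whole analysis: "The data in this single arm study will be described by descriptive statistics only, using binomial confidence where necessary". Section 10.3 repeats it and illustrates precision at a 5% failure rate: "we find an upper limit 95% CI of 6.54% with 1000 patients", and 6.05% with 2000.

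Section 10.2 draws on a cited paper. It says the upper 95% limit should be quoted for all results, and that a limit above 2.5% "should generally lead to a conclusion that the device is poor or unsuitable for clinical use". It adds: "We followed all of these conclusions". No formal pass/fail test is set.

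On who inserts the device, section 7.2 says "the investigator will examine their operating list and decide if the operations are suitable for the LMA Protector", and sections 7.1 and 7.2 make the investigator the anaesthetist for the case. Section 5 names five centres and lists among the data to be collected "a) investigator name, b) number of previous insertions of the device by the investigator". Section 3 says investigators will be "anaesthetists with experience of using similar airway devices more than 200 times", and section 14.1 says "Each researcher is a consultant with an NHS contract". Section 3 also says this device is not in standard care at any participating trust.

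Under section 11.2 each site sends its spreadsheet to the lead team at the end of data collection, with study IDs and nothing identifiable.

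**The concern.** The three primary outcomes are first-go insertion, first-go ventilation and complication-free insertion. All plausibly depend on who holds the device. With 1100 to 2000 patients at five centres, each recruited by the anaesthetist doing the case, the same operators will contribute repeatedly. If some operators fail more often than others, 1100 insertions carry less information than 1100 independent ones, and a simple binomial interval is too narrow.

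The upper limit is the quantity section 10.2 says to quote and links to a 2.5% benchmark, so an understated limit could make the device look better established than it is. Section 10 names no clustering term, robust variance or operator summary, although investigator identity is recorded.

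**Working it through.** **1. Reproduce the stated limits.** The exact (Clopper-Pearson) upper limit is the 0.975 quantile of Beta(x + 1, n − x).

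- 50/1000: 6.54%, as stated.
- 100/2000: 6.05%, as stated.
- At the planned interim size, 55/1100 gives 6.46% and 110/1100 gives 11.93%.
- Against 2.5%, 17/1100 gives 2.46% and 18/1100 gives 2.57%. So 17 failures (17/1100 = 1.55%) is the most that stays below 2.5%.

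**2. Inputs the documents do not give.** These are the number of operators k and the ICC. Assumed range: k = 20, 40 or 110 with equal caseloads, and ICC 0.001 to 0.05.

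**3. Allow for clustering.** Design effect DE = 1 + (n/k − 1) × ICC. The adjusted limit is the exact limit computed on x/DE failures in n/DE patients. Example: k = 20, ICC 0.05 gives DE = 1 + (55 − 1) × 0.05 = 3.70. Then n/DE = 1100/3.70 = 297.3, x/DE = 55/3.70 = 14.9, and the limit is 8.13%.

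| Operators | ICC | DE | Limit, 55/1100 | Limit, 17/1100 | Most failures below 2.5% |
|---|---|---|---|---|---|
| any | 0 | 1.00 | 6.46% | 2.46% | 17 |
| 110 | 0.001 | 1.01 | 6.47% | 2.47% | 17 |
| 110 | 0.01 | 1.09 | 6.53% | 2.51% | 16 |
| 110 | 0.05 | 1.45 | 6.80% | 2.70% | 15 |
| 40 | 0.001 | 1.03 | 6.48% | 2.48% | 17 |
| 40 | 0.02 | 1.53 | 6.86% | 2.74% | 14 |
| 40 | 0.05 | 2.33 | 7.37% | 3.11% | 12 |
| 20 | 0.001 | 1.05 | 6.50% | 2.49% | 17 |
| 20 | 0.01 | 1.54 | 6.86% | 2.75% | 14 |
| 20 | 0.05 | 3.70 | 8.13% | 3.69% | 8 |

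Over the same range the plan's 6.54% (n = 1000) becomes 6.55% to 8.18%, and its 6.05% (n = 2000) becomes 6.06% to 7.90%.

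**4. Which readings against 2.5% could change.** None at ICC 0.001. At 110 operators and ICC 0.01, only 17 failures. At 40 and 0.02, 15 to 17. At 20 and 0.05, 9 to 17. At 5% and 10% the simple limits (6.46% and 11.93%) already exceed 2.5%.

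**5. Coverage of the upper limit.** Beta-binomial simulation, 40,000 runs, n = 1100, true rate 5%, nominal 0.975. The clustered limit uses an ICC estimated from each simulated data set, with DE not below 1.

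| Operators, ICC | Simple limit | Clustered limit |
|---|---|---|
| independence | 0.980–0.982 | 0.983–0.984 |
| 110, 0.01 | 0.977 | 0.980 |
| 40, 0.02 | 0.953 | 0.971 |
| 20, 0.05 | 0.853 | 0.953 |

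The exact limit is slightly conservative, which absorbs small clustering. With unequal caseloads (coefficient of variation 0.66, 40 operators, ICC 0.02) the simple limit covers 0.942 and the clustered limit 0.971.

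**The case against.** The plan contains no arithmetic error. It describes a single-arm observational study with descriptive statistics and no formal test. Point estimates and recruitment are unaffected. Operators are experienced consultants, which makes low clustering plausible. The size of the effect depends entirely on inputs the documents do not supply. All of this stands, and it is why the point is an optional improvement.

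The remedy is also weakest where a reading could change. With so few failures the ICC is poorly estimated: in simulation at a true rate of 1.55%, with 9 to 17 failures and a true ICC of 0.01, the estimate was zero or negative in 28% of runs (40 operators) and 35% (110). This stands too, so the added interval should be labelled as a sensitivity result.

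Three stronger readings are not supported:

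- A reader might infer that 6.54% and 6.05% are wrong. They are correct exact limits under independence.
- A reader might infer that operator data have no place in the analysis. Section 10.1 covers the study data descriptively, and section 5 lists investigator and previous insertions among them. The accurate statement is that section 10 names no analysis by operator.
- A reader might infer that operator identity will be lost on pooling. Section 11.2 is concerned with participant identity, and nothing says the investigator field is removed. It is only not assured.

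One part of the objection does not hold. Experience in section 3 is with similar devices, and this device is not in standard care at the participating trusts, so differences between operators while learning it remain plausible.

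**Conclusion.** The concern holds in conditional form, as an improvement the sponsor could make. Sections 10.1 and 10.3 rely on independence, the design has the same anaesthetists inserting the device repeatedly, and clustering by operator would make the quoted upper limit too low. The assumed range runs from no visible effect (6.46% to 6.47% for 55/1100) to 8.13% in an extreme corner, with little or no shortfall when the ICC is low or operators are many.

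A reader might infer that clustering is present here, or that it would overturn the study's conclusion about the device. The documents show neither. They give no operator numbers and no ICC, and the reading against 2.5% is open only for about 9 to 17 failures in 1100, most of that band needing the extreme corner.

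**What to change.** In section 10, keep the exact binomial limit. For each of the three primary outcomes, report beside it one pre-specified 95% interval allowing for clustering by investigator:

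- Interval: the exact limit on failures and patients both divided by the design effect.
- Design effect: 1 + (sum of squared caseloads / n − 1) × ICC, which allows for unequal caseloads. Estimate the ICC from the data by a named method, such as the ANOVA estimator. Set the design effect to 1 if the formula gives less than 1 or the ICC cannot be estimated.
- Context: report the number of operators and their caseloads.
- Label: state that it is a sensitivity interval and is imprecise when failures are few.

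In section 11.2, specify that a pseudonymous investigator code stays in the spreadsheet sent to the lead team.

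The cost is a little more analysis and one coded column, with no new patient data. The added interval may be wider than the simple one. It does not fully restore coverage with few operators and a high ICC (about 0.95 against 0.975 at 20 operators, ICC 0.05).
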